Study Title: Effectiveness of KeraStat Gel for Improved Cosmesis of Partial Thickness Burns

NCT03564795

SUMMARY	2
BACKGROUND, RATIONALE AND CONTEXT	2
BACKGROUND.....	2
RATIONALE.....	3
OBJECTIVES	3
METHODS AND MEASURES	4
DESIGN.....	4
SETTING.....	6
SUBJECTS SELECTION CRITERIA.....	6
INTERVENTIONS AND INTERACTIONS.....	7
AGENT DESCRIPTION	7
AGENT ADMINISTRATION.....	8
SCHEDULE OF EVENTS	9
STUDY SUBJECT WITHDRAWAL	14
ANALYTICAL PLAN.....	14
HUMAN SUBJECTS PROTECTION	15

Summary

This study seeks to determine whether the use of KeraStat Gel as the primary dressing for partial thickness burns (1) results in improved healed wound cosmesis and (2) results in less painful dressing changes, faster reepithelialization, and reduction in need for excision and grafting. The study design is a within subject control. Each of two distinct burns will be randomized to the use of KeraStat Gel or standard of care (SOC). The length of study participation for a subject is 1 year. Subjects complete 2 office visits and 2 remote visits during the first month then office visits at months 3, 6, and 12 post burn.

Subjects will complete a visual analog scale for pain during dressing changes, and the reepithelialization of the wound will be noted. During remote visits on days 7 and 21, subjects may complete a digital VAS scale and collect a photo of the wound. At months 3, 6, and 12, subjects and study personnel will complete the Patient Observer Scar Assessment Scale (POSAS). During month 3, 6, and 12 visits, the scars will be subjected to measurement of transepidermal water loss (TEWL) measured with a Tewameter. The wound sites will be photographed at each site visit.

Background, Rationale and Context

Background

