Ingredients: Water (Aqua), Oxidized Keratin, Carbopol, Phenoxyethanol, Ethylhexylglycerin, and Sodium Hydroxide. KeraStat Gel is for topical use only and should not be swallowed. Subjects should avoid contact with eyes. If swallowed, seek medical attention. If symptoms worsen or persist, consult a physician.

Agent Safety Data

KeraStat Gel has been subjected to a full suite of ISO 10993 safety testing (Table 1).

Table 1. Summary of Completed ISO 10993 Testing

Test ^{a,b}	Method	Test System	Route	Testing Outcome
Cytotoxicity	ISO 10993-5	Mouse fibroblast CCL-1 (L929)	In vitro	Non-cytotoxic
Sensitization	ISO 10993-10	Guinea Pig	Topical In vivo	Non-sensitizing
Irritation	ISO 10993-10	Rabbit (NZ White)	Intracutaneous In vivo	Mild-Moderate Irritant
Acute Systemic Toxicity (3 day)	ISO 10993-11	Mouse (Swiss Albino)	Intraperitoneal In vivo	Non-toxic
Subacute Systemic Toxicity (28 day)	ISO 10993-11	Rat (Albino)	Subcutaneous In vivo	Non-toxic

Pyrogenicity	ISO 10993-11	Rabbit (NZ White)	Intravenous In vivo	Non-pyrogenic
--------------	--------------	----------------------	-------------------------------	---------------

Performance testing, including *in vivo* testing of its application to burn wounds, supports the safety and reliable quality of this device. Two clinical studies have also supported product safety. This product is approved by the U.S. Food and Drug Administration (FDA) (K162759).

Agent Administration

In this clinical trial, subjects will apply KeraStat Gel as directed by the physician per institutional SOC guidelines. We anticipate that the medical care team or subject will clean and dress the wound every 1 to 3 days. KeraStat Gel should be changed at least every 3 days but can be changed as often as the Investigator feels is necessary. The wound should first be cleansed and debrided according to the institutional SOC guidelines. Following cleansing, KeraStat Gel should be applied uniformly, providing a coating across the entire surface of the burn and past the edge of the burn. On average, one tube of KeraStat Gel will cover 0.5% TBSA. At the time of dressing changes, KeraStat Gel should be removed with soap and water and gauze wiping (as necessary), reapplied, and covered with a secondary dressing of petrolatum gauze. Treatment will continue until full reepithelialization (100%) is achieved.

Interactions

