At baseline, demographic and medical history will be collected, and inclusion/exclusion criteria will be confirmed. If the subject meets these criteria, vital signs will be collected, and the wounds will be randomized to treatment including KeraStat Gel dressings or SOC. Two burns identified by the Investigator will be labeled Burn A and Burn B by study staff and noted on the Case Report Form (CRF). The randomization scheme will be generated in nQuery Advisor 7.0 in advance by the study statistician. An adequate, sequentially numbered, opaque, sealed envelope set will be produced prior to the implementation of the protocol for the site to use. These envelopes will be shipped and maintained at the site with the trial staff member designated by the Investigator or the Investigator themselves to conduct randomization. The staff will choose the first envelope in sequence, record the subject ID and date of the randomization on the outside of the envelope. They will open the envelope and reveal the index card with the treatment assignment for Burn A and Burn B, record again the Subject ID and randomization date on that card, and then upload a photo of the completed card with the Subject's source documentation for the clinic visit. No subject may be randomized early into the study. All envelopes at each site must be used in sequential order. Any alterations to this procedure will be considered a protocol violation. Burns will be examined and photographed. The subject will be asked to complete the Visual Analog Scale (VAS) pain score for each burn site on study. Once each treatment is applied, the subject will once again complete the VAS pain score for each burn site. Thus, two VAS pain scores will be collected for each burn at each treatment application by study staff.

Hospital staff will change dressings until the subject is discharged from the hospital. At discharge, the burns will once again be examined and photographed. The subject will be asked

Protocol version: 5

Template updated 5 Jul 2021

to complete the Visual Analog Scale (VAS) pain score for each burn site on study. Once each treatment is applied, the subject will once again complete the VAS pain score for each burn site. Subjects will be provided with enough KeraStat Gel-related dressings to last 17 days. Subjects will be instructed on dressing changing procedures for both burns per institutional SOC guidelines.

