Dressings will be changed per institutional SOC guidelines but at a minimum of every 3 days. Subjects will return to the clinic on days 14 ± 3 and 28 ± 3 post-enrollment for the first 4 weeks and at months 3 (± 7 days), 6 (± 7 days), and 12 (± 14 days) post-enrollment. Subjects will also participate in a remote visit on days 7 ± 3 and 21 ± 3 post-enrollment. Dressing changes will be continued until reepithelialization is achieved. During each visit, study staff will document the number of dressing changes that occurred outside of clinic visits as well as any pertinent information related to the dressing changes. During visits when dressing changes are still necessary, subjects will complete the VAS pain score before and after dressing changes to each burn, and any unanticipated adverse events related to the device will be logged. Subjects who are able and willing will download an application on their smartphone that will prompt them to record the VAS pain score before and after dressing changes will complete this during remote visits on days 7 and 14. Subjects will also be asked to upload photos of the burns at days 7 and 21 utilizing the medical center's MyChart application. Appearance of the sites will be assessed at months 3, 6, and 12 using the POSAS. During the visits at 3, 6, and 12 months, sites will be subjected to 3 measurements of TEWL. Photographs will be obtained at all in-person visits and may be subjected to wound closure and percent epithelialization measurements via ImageJ. Recording of adverse events (AE), measurement of vital signs, examination of the wound/site of wound, and notation of concomitant medication and procedures will also take place during each visit. All measures will be completed if an individual agrees to a final visit after withdrawal from the study.

Masking

This study will be an open-label study.

Schedule of Events

Baseline Testing (All subjects)

- Photographs (prior to start of treatment)
- Vital signs (e.g., blood pressure, heart rate, temperature, height, weight)
- Examination of wound, including wound measurement
- Concomitant medications
- VAS pain score before and after dressing application

Discharge

- Adverse events

- Vital signs
- Examination of wound, including wound measurement and percent reepithelialization
- Photography of treatment site
- Concomitant medications and procedures
- Dressing change
- VAS pain score before and after dressing change

Day 7, 21 (± 3 , Remote visit)

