The VAS pain score⁸ is a simple, widely used instrument that has been utilized for pain assessments since the 1970s. It will be administered by site personnel during a clinic visit. The VAS will also be completed during dressing changes at home on days 7 and 21 by subjects who agree to the use of an at-home phone application. This unidimensional measure is composed of a line, usually 10 centimeters in length, anchored by two verbal descriptors representing the symptom extremes (“no pain” and “worst imaginable pain”) and 6 facial expression anchors. The respondent places a line perpendicular to the VAS line that represents their pain intensity. The distance between the “no pain” anchor and the subject’s mark is measured in cm, providing a range of scores from 0 to 10.

TEWL⁹ has been shown to be strongly correlated with hypertrophic scar values and erythema. It will be measured using a tewameter. The scar area will be measured three times by placing the probe perpendicular without pressure on the area of interest with the surface area in horizontal position. The three individual measurements will be recorded.

The POSAS⁸ is a reliable and complete scale that takes into account the judgment of both the subject and the Investigator. It will be administered by site personnel during a clinic visit. The subject form provides space for indicating the scar location and includes seven questions, which are answered using a numerical scale anchored by two verbal descriptors representing the symptom extremes or agreement. Similarly, the observer assessment scale provides space for indicating the location of the scarring. It includes seven parameters that are scored using a numerical scale anchored by two verbal descriptors representing the symptom extremes (“normal skin” to “worst scar imaginable”). These are further described by pre-defined categories.

⁸ Fearmoni, R.; Bond, J.; Erdmann, D; Levinson, H. A review of scar scales and scar measuring devices. *Eplasty*. 2010; 10:e43.

⁹ Gardien, K.; Baas, D.; de Vet H.; Middelkoop, E. Transepidermal water loss measured with the Tewameter TM300 in burn scars. *Burns*. 2016; 42(7):1455-1462.

Protocol version: 5

Template updated 5 Jul 2021

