For the primary objective of the study, improved cosmesis will be analyzed using data from the POSAS, as a total score, and separately for the observer score and then the subject score. Changes from baseline will be examined at 3 months, 6 months and again at 1 year post treatment. TEWL will be considered at 3 months, 6 months, and 1 year. This analysis may also consider the baseline status of the burn including depth, surface area, location of the burn injury and subject baseline characteristics (age, concomitant injury).

Protocol version: 5

Template updated 5 Jul 2021

Secondary objectives include determining whether KeraStat Gel wound dressing results in less painful dressing changes, faster reepithelialization, and reduction in need for excision and grafting. Improvement in pain will be assessed using the scoring from the VAS pain scale at Screening, Days 7, 14, 21 and 28. Box plots of the VAS pain scores will be presented displaying the medians and quartiles in each treatment group over time. A nonparametric test will be used to determine changes in the score across time (Kruskal-Wallis) as well. Reductions in excision and grafting will be analyzed by treatment groups using the same methods as the VAS pain score. Median time to 100% reepithelialization by study treatment group will be conducted, mean times (days) will be analyzed using a Wilcoxon test by treatment groups, as well as a time to event analysis for 90% or higher reepithelialization from baseline.

The incidence of adverse events will be reported and summarized by treatment group. Adverse events will be coded in MedDRA by system organ class and preferred terms (PT).

Human Subjects Protection

Subject Recruitment Methods

Subjects who present at the Burn Center at WF or UMC with qualifying burns as determined by the Investigator will be approached for inclusion in the study by study personnel.

Remuneration

Enrolled study subjects will be provided with one \$45 gas card per visit for office visits on days 14 and 28 and months 3, 6, and 12.

Informed Consent

All subjects must give their informed consent in accordance with the informed consent regulations in Title 21 CFR, Part 50. Each subject over 18 years and subjects under 18 and their legally authorized representative will execute written informed consent (and assent if applicable) before any study procedures are conducted. Study personnel will obtain written informed consent in the clinic.

Confidentiality and Privacy

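### The pain analysis names no VAS score and tests change over time, so as written it does not compare dressing-change pain between a subject's two burns

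*Combined protocol and SAP*

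**What the plan says.** The objective appears under Objectives and again in the Analytical Plan: "Secondary objectives include determining whether KeraStat Gel wound dressing results in less painful dressing changes, faster reepithelialization, and reduction in need for excision and grafting".

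Two descriptions of the VAS timing appear in the documents.

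- **Before and after.** Under Interactions, a first score is taken for each burn at baseline and then "Once each treatment is applied, the subject will once again complete the VAS pain score for each burn site". The section sums up: "Thus, two VAS pain scores will be collected for each burn at each treatment application by study staff". For later visits it says "subjects will complete the VAS pain score before and after dressing changes to each burn", and it has the phone app prompt for the same two time points. The visit lists in the Schedule of Events agree.
- **During.** The Summary says "Subjects will complete a visual analog scale for pain during dressing changes". The description of the VAS under Outcome Measure(s) says "The VAS will also be completed during dressing changes at home on days 7 and 21".

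That description gives the end anchors of the scale. It gives no recall period and no instruction to rate pain felt during the change.

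Agent Administration describes what happens between the two scores. The wound is cleansed and debrided, and at a change "KeraStat Gel should be removed with soap and water and gauze wiping (as necessary), reapplied".

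The Analytical Plan then says "Improvement in pain will be assessed using the scoring from the VAS pain scale at Screening, Days 7, 14, 21 and 28". It adds box plots by treatment group over time and a Kruskal-Wallis test for changes across time. It defers further detail to a separate SAP, to be finalised before database lock, which is not among these documents.

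**The concern.** The question is whether changing the dressing hurts less on the gel burn than on the Mepilex Ag burn of the same person. That needs a score that reflects the change, and a comparison of that score between the two burns. The plan fixes neither.

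Two problems follow. First, pain from a partial thickness burn would be expected to fall over four weeks under either dressing. A significant test across visits would therefore be likely whether or not the dressings differ, and it could be reported as an improvement in pain. Second, the steps most likely to hurt (removal, wiping, cleansing, debridement) fall between the two scores. If subjects answer the second score for how they feel under the new dressing, part or all of the pain of the change goes unrecorded. A later SAP can still choose the variable and the test. It cannot change what subjects were asked.

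**Working it through.** **Figures in the plan.** The documents give no alpha, power, effect size or SD for pain, so there is no stated result to reproduce. The only related figure, 30 subjects × 2 burns = 60 wounds, is correct.

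**Step 1: score against objective.** Two scores per burn per change are planned, before and after. The Analytical Plan refers only to the VAS scoring at each visit. Three variables fit that wording: before, after, and after minus before. Only the last two carry information about the change.

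**Step 2: test against objective.** The between-dressing element is a box plot, which is descriptive. The named test is across time. To see what it responds to, one arm was simulated with 30 subjects and five visits. All inputs are assumptions: mean starting pain 5 cm, between-subject SD 1.5, within-burn SD 1.5, scores limited to 0–10, and Kruskal-Wallis across visits at 0.05.

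| Fall in pain per visit | Rejection rate, no gel benefit | Rejection rate, constant 2 cm gel benefit |
|---|---|---|
| 0 cm | 0.003 | 0.001 |
| 0.5 cm | 0.916 | 0.905 |
| 1 cm | 1.0 | 1.0 |

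The rate depends on the fall over time and hardly at all on the gel benefit. The first row also lies far below 0.05, because the test treats repeated scores from one subject as independent.

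**Step 3: what the planned scores could show if paired.** Assume mean pre-change pain of 3 cm on both burns, SDs as above, and change-related pain of 4 cm with Mepilex Ag and 2 cm with gel, so the true difference is 4 − 2 = 2 cm. Let p be the share of that pain still reported at the after score. The subject effect cancels between burns.

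- After score: mean difference 2p, SD 1.5 × √2 = 2.12, ratio 2p/2.12 = 0.94p.
- After minus before: mean difference 2p, SD 1.5 × √4 = 3.0, ratio 2p/3.0 = 0.67p.

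Simulated power of a signed-rank test at one visit with 30 pairs, two-sided 0.05:

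| p | After score | After minus before |
|---|---|---|
| 0 | 0.06 | 0.05 |
| 0.25 | 0.21 | 0.14 |
| 0.50 | 0.68 | 0.41 |
| 0.75 | 0.95 | 0.76 |
| 1 | 1.00 | 0.94 |

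The pre-change score alone stays near 0.05, because it was assumed equal on both burns. Subtraction does worse here because the errors of the two scores were assumed independent. If they were strongly correlated within a burn, subtraction would do better. A fitted covariate lets the data decide between these cases; it was not simulated.

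**The case against.** The strongest reply is that the design is sound and only the write-up is thin. Each burn has scores on either side of the change, the control is within subject, and a separate SAP can name the variable. The sentence on excision and grafting, which borrows the pain methods by treatment group, suggests that a between-dressing analysis was intended. Most of this stands, and it limits the point in three ways.

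- A reader might infer that the trial cannot show whether changes are less painful. The documents do not support that. A paired contrast of the after score, or of after minus before, can be computed from planned data. It may lose sensitivity, but it is not impossible.
- A reader might infer that the first score is resting pain. The text says only that it is taken before the change. After the first application it is also taken under the assigned dressing, so it is not pure background.
- A reader might infer that before and after scores will be averaged and the difference diluted. No section says so. The score is unspecified, and no dilution figure follows.

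It is also fair that the VAS form and app prompts are not shown. That subjects would answer for pain at that moment is plausible, but it is an inference.

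The reply does not supply a test. Intent by treatment group is visible, but no paired comparison is stated. Kruskal-Wallis on two dressing groups would ignore that both burns belong to one person. The conflict between during and before/after also remains open.

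**Conclusion.** The point holds as a gap in specification, with a measurement risk attached. As written, the only named pain test detects change over time. It does not compare dressing-change pain between a subject's two burns, and the VAS timing is described in two ways that do not agree.

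The finding about the test rests on the text alone. How much sensitivity the after score loses depends on how much of the pain persists until it is taken. The documents do not give that, so the 0.06 to 1.00 range is an illustration on assumed pain levels and SDs. It also assumes all 30 pairs. Scores are taken only while dressing changes are still needed, and the Design section expects closure within 21 days, so later visits will have fewer pairs. This is a secondary objective, and the primary cosmesis question is not affected.

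**What to change.** 1. **Reconcile the timing** in the Summary, Interactions, Schedule of Events and Outcome Measure(s). State once when each score is taken, and whether each burn is scored as soon as it is redressed or only after both are done. Also resolve the app days: one sentence in Interactions gives 7 and 14, while other text gives 7 and 21.
2. **Replace the across-time Kruskal-Wallis test** as the test of this objective. Use a within-subject comparison, KeraStat Gel burn against Mepilex Ag burn, of the post-change VAS adjusted for the pre-change VAS at the same visit. A mixed model with a subject effect over visits would do this. A signed-rank test per visit is a simpler alternative, applied to a within-subject difference that takes the pre-change score into account. Present pre-change scores separately, and use the Screening score taken before application only as baseline. Show the unadjusted contrast too, because later pre-change scores are themselves taken under the assigned dressing. State how visits are handled when only one burn still needs dressing, and whether the discharge scores, which are collected but not listed for analysis, are used.
3. **Anchor the second score.** Add one line to the VAS form and the app asking for the worst pain in that burn during the change just completed.

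Item 2 costs only analysis text and uses data already planned. Item 3 needs an amendment to the form and app but no added visit or score. Its downside is recall over a few minutes for two burns, including in children from age 6. If subjects are already enrolled, which the documents do not say, scores collected before the amendment must be flagged and analysed separately or with a term for the form version.

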⁷ Bloemen, M.C.T., et al., Prevention and curative management of hypertrophic scar formation. *Burns*, 2009. 35(4): p. 463-475.

Protocol version: 5

Template updated 5 Jul 2021

Methods and Measures

Design

This study is a randomized, controlled, within-subject trial examining the effectiveness of KeraStat Gel, as compared to the institutional SOC, Mepilex Ag, in improving wound cosmesis. Once the Investigator has determined the subject is a candidate for inclusion in the study, the subject will be approached about enrolling in this study. A total of 30 burn subjects presenting to the Burn Centers will be enrolled.

Upon presenting to the hospital, potential study subjects will be assessed for inclusion and approached for consent, as appropriate. Once the subject and/or legal guardian has consented to participate in the study, baseline assessments can be completed. We anticipate that the majority of subjects presenting with burns that qualify for inclusion in the study will have at least one night stay in the hospital; however, this is not criteria for inclusion. KeraStat Gel and Mepilex Ag will each be randomized to application on one of two identified burn sites on the subject, Burn A or Burn B. All subjects will have one burned area dressed with KeraStat Gel and a second area dressed with Mepilex Ag per SOC. The Investigator or study staff will initially apply the dressings per a computer-generated randomization scheme. The burn dressed with KeraStat Gel will have a secondary dressing of petrolatum gauze and telfa. For subjects who have more than two burns, all additional burns will be treated according to the physician's discretion. Subjects will be provided with enough KeraStat Gel and KeraStat Gel-related dressing supplies upon hospital discharge to accommodate prescribed dressing changes until their next visit. The Investigator will instruct subjects on dressing changes as required by institutional SOC guidelines and instructions for use of KeraStat Gel prior to discharge. The need to maintain treatment consistency will be stressed; Burn A and Burn B should always receive their designated dressing.

For the first 4 weeks, subjects will have weekly visits with site staff. On days 7 and 21, this visit will be remote. On days 14, and 28, this visit will be an office visit.

[figure not shown]

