Below is a schematic overview of the study.

Optional at-home questionnaire and photographs at virtual visits on weeks 1 and 3

Wound assessments, questionnaires, photographs, TEWL assessment at 3 months, 6 months, 1 year

Setting

This study will be conducted in the Wake Forest (WF) Burn Center and in the University Medical Center New Orleans (UMC). Subjects may continue treatment as inpatients or as outpatients.

Subjects Selection Criteria

- **Inclusion Criteria**

- Males and females, age 6 years and older
- Written informed consent and assent, if applicable (including parent if subject is a minor)
- Presenting with at least two comparable, discrete, and separate partial thickness thermal burns, as determined by the Investigator, measuring 50-1,000 cm² each
- Study wounds identified are partial thickness depth
- KeraStat Gel and Mepilex Ag can be applied to the randomized study burn wounds as definitive care treatment within 72 hours from time of injury
- Overall total body surface area (TBSA) burned < 20%

- **Exclusion Criteria**

- Pregnant or nursing
- Prisoner
- Presence of inhalation injury, as determined by the Investigator
- Injury requiring formal intravenous fluid resuscitation
- Concomitant non-thermal traumatic injuries
- Chronic medical conditions including, but not limited to, documented > renal impairment (Cr > 2.5 mg/dL), hepatic impairment (Total bilirubin > 2.5 mg/dL), thromboembolic disorders, active infection in study wound areas, uncontrolled diabetes (HbA1C > 7%), HIV infection, history of melanoma or systemic malignancy within the last 10 years
- Receiving corticosteroids, immunosuppressive agents, radiation or chemotherapy, topical growth factors, or any other medication the Investigator feels will affect wound healing
- Not expected to live at least 13 months post-burn
- Previously treated with a skin graft at either of the treatment sites

- Chemical or electrical burn
- Proposed study wounds are full thickness
- Any condition the Investigator determines will compromise subject safety or prevent the subject from completing the study

- **Sample Size**
The study size is 30 subjects, two wounds per subject, 30 wounds per treatment cohort resulting in 60 total wounds.

Because this trial is designed to examine long-term outcomes, no interim analyses or stopping rules are planned.

Interventions and Interactions

Intervention: KeraStat Gel

Agent description

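### The pain analysis does not adjust for each burn's pre-application Day 0 VAS, giving up precision that is nearly free

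*Combined protocol and SAP*

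**What the plan says.** - **Pain analysis** (Analytical Plan, secondary objectives): "Improvement in pain will be assessed using the scoring from the VAS pain scale at Screening, Days 7, 14, 21 and 28". The display is "Box plots of the VAS pain scores will be presented displaying the medians and quartiles in each treatment group over time". The test is "A nonparametric test will be used to determine changes in the score across time (Kruskal-Wallis) as well". No paired comparison of dressings, change-from-Screening definition or covariate is given for pain.
- **Baseline adjustment elsewhere**: the preceding paragraph, on POSAS and TEWL, allows burn and subject characteristics to be considered. That is optional, belongs to the cosmesis analysis, and does not list VAS.
- **Data collected**: the Schedule of Events lists, at baseline, "VAS pain score before and after dressing application". The Interactions section confirms that "two VAS pain scores will be collected for each burn at each treatment application by study staff". Each burn therefore has one Day 0 score before its first study dressing and one after.
- **Design**: "All subjects will have one burned area dressed with KeraStat Gel and a second area dressed with Mepilex Ag per SOC". The Sample Size section reads: "The study size is 30 subjects, two wounds per subject, 30 wounds per treatment cohort resulting in 60 total wounds". It gives no alpha, power, effect size, SD or correlation.
- **Separate SAP**: the Analytical Plan says one will be finalised before database lock. It is not among the documents reviewed.

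**The concern.** Two burns on one person can hurt differently before any study dressing is applied. Eligibility asks for comparable burns in the Investigator's judgement, but allows 50 to 1,000 cm² each and sets no limit on a difference in pain. Pairing removes differences between subjects. It does not remove differences between the two burns of one subject, and the pre-application Day 0 score is the only direct pain measurement of those.

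As written, that score appears only as one more point on the time axis. Neither a box plot nor a Kruskal-Wallis test can use it as a covariate. At stake are the width of the confidence interval for the dressing difference, and how a result should be read if one set of burns happened to start out more painful.

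**Working it through.** **The plan's own figure.** 30 subjects × 2 burns = 60 wounds, which agrees with the Sample Size section. No power calculation is stated, so there is none to reproduce. Every SD and correlation below is an assumption, shown over a range.

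**1. Chance imbalance in starting pain.** Let s be the SD of Day 0 VAS (0 to 10 cm scale), c the correlation between two burns on one subject, and n = 30 pairs.

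SE of the mean baseline difference = s × √(2(1 − c)/30)

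| s (cm) | c | SE (cm) | 95% range (± 1.96 SE) |
|---|---|---|---|
| 1.5 | 0.8 | 0.17 | ± 0.34 |
| 2.0 | 0.5 | 0.37 | ± 0.72 |
| 3.0 | 0.3 | 0.65 | ± 1.27 |

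In the middle case, the chance of an imbalance above 0.5 cm is 17%. These figures describe imbalance at baseline, not error in the later comparison. With equal SDs only a fraction rho carries forward, so 0.72 cm becomes 0.3 × 0.72 = 0.22 cm at rho = 0.3, or 0.5 × 0.72 = 0.36 cm at rho = 0.5.

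**2. Precision gained by adjustment.** Let rho be the correlation between the within-pair baseline difference and the within-pair follow-up difference.

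- Variance relative to an unadjusted paired comparison = 1 − rho².
- Equivalent unadjusted pairs = 30/(1 − rho²).
- Allowing for estimation of the slope, multiply the variance by 1 + 1/(n − 3) = 1 + 1/27 = 1.037.
- Power is two-sided at 0.05 from the noncentral t with 28 df, for an effect that 30 unadjusted pairs detect with 80% power, before the slope factor.

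| rho | 1 − rho² | Equivalent pairs | Power | Variance with slope factor |
|---|---|---|---|---|
| 0.2 | 0.96 | 31.2 | 0.815 | 0.996 |
| 0.3 | 0.91 | 33.0 | 0.835 | 0.944 |
| 0.5 | 0.75 | 40.0 | 0.898 | 0.778 |
| 0.7 | 0.51 | 58.8 | 0.975 | 0.529 |

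After the slope factor the gains are about 0.4%, 6%, 22% and 47%. Break-even is where (1 − rho²) × 28/27 = 1, that is rho = √(1/28) = 0.19. At rho = 0 the loss is 1/27 = 3.7%.

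**3. Fewer pairs.** With 15 pairs (an assumption, for a visit with optional or post-healing scores), the factor is 1 + 1/12 = 1.083. Break-even moves to √(1/13) = 0.28 and the largest loss to 8%.

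**4. Conditional error.** If the baseline imbalance happens to be 1.96 SE, an unadjusted paired test with no true effect rejects in about 6%, 8%, 13% and 21% of cases at rho = 0.2, 0.3, 0.5 and 0.7. Averaged over all randomisations the rate stays at 5%.

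**5. The named test.** In a simulation with no dressing effect and a 3 cm fall in pain over five time points (4,000 runs, 30 subjects), Kruskal-Wallis across time rejected in 100% of runs within each arm. It detects the time trend. It neither compares the dressings nor adjusts for baseline.

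**The case against.** **Improvement implies a reference value.** Assessing improvement, or change across time, needs a starting point, so Screening may be intended as baseline rather than outcome. That reading is open. But no change score is defined, and the plan does not say which of the two Screening scores would serve. With equal SDs a change score has relative variance 2(1 − rho), which is worse than no adjustment when rho is below 0.5.

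**The missing paired test is the larger fault.** This stands. The power figures above start from a paired comparison that the plan does not name. Substituting a paired test alone would still leave starting pain unadjusted.

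**Thirty pairs is a ceiling.** This also stands. Day 7 and Day 21 VAS is optional. Under Interactions, in-clinic VAS belongs to visits where dressing changes are still needed, and the Design section expects burns not requiring grafting to close within 21 days.

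**The gain may be small.** Comparable burns and progressive healing could both keep rho low. The documents cannot settle this.

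**The baseline score may not be clean.** Interactions describes the envelope being opened before it describes the first VAS, in an open-label study. The narrative may not be strictly chronological: it also places baseline photographs after randomisation, whereas the photography instructions require them before. No such rule covers VAS.

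A reader might go further and infer that the pain comparison is biased, that starting pain is a main source of noise, or that counting Screening dilutes an averaged effect. The documents support none of these. Randomisation within subject removes average bias, no variance components are given, and no averaging over visits is specified.

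**Conclusion.** The point holds as one of precision and conditional imbalance in a secondary endpoint. The plan collects a pre-application pain score on every burn and does not commit to using it to adjust the dressing comparison. After the slope is estimated, the gain with 30 pairs runs from almost nothing at rho = 0.2 to nearly half the variance at rho = 0.7. It is smaller, and can turn into a slight loss, at visits with few pairs. These sizes assume a paired analysis with an approximately linear relation between baseline and later differences. The conclusion that the score goes unused rests on the text alone. The separate SAP could still add the adjustment.

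**What to change.** In the SAP, before database lock:

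- Name each burn's pre-application Day 0 VAS as the baseline covariate, and do not count it as an outcome time point. For subjects still to be enrolled, require it to be recorded before the envelope is opened.
- Keep the post-application Day 0 score as an outcome. It follows the first study dressing and bears on the dressing-change pain objective.
- At each follow-up visit, regress the KeraStat-minus-Mepilex VAS difference on the KeraStat-minus-Mepilex difference in pre-application Day 0 VAS. The intercept is the dressing difference at equal starting pain. An equivalent within-subject mixed model using all available burns would also serve, and would make use of subjects with a score for only one burn.
- State which follow-up score (before or after the dressing change) is analysed. Report the adjusted difference with a 95% CI and the number of pairs at each visit.
- Keep the box plots, including Screening.

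The cost is SAP wording, one instruction on the timing of the first score, and one degree of freedom. No new measurement is needed. With 30 pairs the worst case is a loss of about 4% of variance if rho is near zero.
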